**Eligibility Criteria:**

Patients must meet all applicable Inclusion and none of the Exclusion Criteria.

Inclusion Criteria:

1. Willing and able to sign the approved informed consent.

2. Age: 18+ years old at Screening.
3. Diagnosis of either PMF per World Health Organization (WHO) diagnostic criteria for myeloproliferative neoplasms (Section 16.2), PPV-MF per the IWG-MRT (Section 16.3), or PET-MF per the IWG-MRT (Section 16.4) and meet the following additional subtype specific criteria:
  - a. Classified as high risk (3 prognostic factors), intermediate risk-2 (2 prognostic factors) or intermediate risk-1 (1 prognostic factor). The prognostic factors, defined by the International Working Group ([Cervantes, et al., 2009](#)):
    - i. Age > 65 years;
    - ii. Presence of constitutional symptoms (weight loss, fever, night sweats);
    - iii. Marked anaemia (Hgb < 10g/dL)\*;
    - iv. **History** of leukocytosis [WBC > 25 x10^9/L (25,000/μL)];
    - v. Circulating blasts ≥ 1%.
- \*A haemoglobin value < 10 g/dL must be demonstrated during Screening for patients who are not transfusion dependent. Patients receiving regular transfusions of packed red blood cells will be considered to have haemoglobin < 10 g/dL for the purpose of evaluation of risk factors.
4. Be refractory or resistant to, inadequately controlled by or intolerant of available approved therapy, or in the Investigator's judgment, are not candidates for available approved therapy (note: approved therapy includes ruxolitinib and, in the US, fedratinib).
5. Eastern Cooperative Oncology Group (ECOG) performance status score ≤2.
6. Peripheral blast count ≤10% prior to dosing on Day 0.
7. Absolute neutrophil count ≥ 0.5 x 10^9/L (500/μL) prior to dosing on Day 0.
8. Platelet count ≥ 100 x 10^9/L (100 k/μL) prior to dosing on Day 0.
9. Life expectancy >36 weeks.
10. Have discontinued all previous therapies for MPNs including ruxolitinib, any chemotherapeutic agents, immunosuppressive therapy (e.g., corticosteroids > 10 mg/day with the noted exception: use of corticosteroids for management of gout is allowed; maintenance supplemental corticosteroid therapy such as prednisone ≤ 10 mg/day or corticosteroid equivalent is allowed), immune modulators (e.g., thalidomide), radiotherapy for at least 2 weeks prior, and interferon for 4 weeks prior to study Day 0. Low dose acetylsalicylic acid is permitted. Palliative radiation treatment to non-index or bone lesions performed < 2 weeks before treatment may be considered with Medical Monitor approval.
11. Amenable to bone marrow evaluation, peripheral blood and urine sampling during the study.
12. Able to swallow capsules.
13. Women of childbearing potential (WOCBP) and fertile men (see Section 6.1) must agree to use an approved method of contraception from Screening until 28 days\* after last IMG-7289 dose. Methods of contraception include: estrogen and progestogen combined hormonal contraception which inhibits ovulation; progestogen-only hormonal contraception associated with inhibition of ovulation; intrauterine device (IUD); bilateral tubal occlusion; vasectomized partner in a monogamous sexual relationship (vasectomy or tubal ligation at least six months prior to dosing); and, complete sexual abstinence (defined as refraining from heterosexual intercourse). Patients practicing abstinence must agree to use an approved method of contraception should they become sexually active during the study.

**Note:** In the UK, males with a pregnant partner must agree to use a condom to avoid exposure to the developing child.

\*The risk of embryofetal toxicity is fully mitigated by 28 days which is >10 half-lives of the drug at the doses used in this study.

Exclusion Criteria:

1. Has undergone major surgery  $\leq 4$  weeks prior to starting study drug or has not recovered from side effects of such surgery.
2. Has undergone any surgical procedure within 2 weeks, excluding minor procedures (e.g., skin biopsy or central venous catheter placement/removal) prior to starting study drug.
3. History of splenectomy.
4. History of or scheduled haematopoietic stem-cell transplant within 24 weeks of screening.
5. Unresolved treatment related toxicities from prior therapies (unless resolved to  $\leq$  Grade 1).
6. Current use of a prohibited medication (e.g., romiplostim) or expected to require any of these medications during treatment with the investigational drug.
7. Known immediate or delayed hypersensitivity reaction or idiosyncrasy to drugs chemically related to IMG-7289 or LSD1 inhibitors (i.e., monoamine oxidase inhibitors; MAOIs) that contraindicates their participation.
8. Current use of monoamine oxidase A and B inhibitors (MAOIs).
9. Uncontrolled active infection.
10. A concurrent second active and non-stable malignancy (patients with a concurrent second active but stable malignancy, such as non-melanoma skin cancers, are eligible).
11. Evidence at the time of Screening of risk of bleeding, including any of the following:
  - a. Activated partial thromboplastin time (aPTT)  $\geq 1.3$  x the local upper limit of normal
  - b. International normalized ratio (INR)  $\geq 1.3$  x the local upper limit of normal
  - c. History of severe thrombocytopenia or platelet dysfunction unrelated to a myeloproliferative disorder or its treatment
  - d. Known bleeding disorder (e.g., dysfibrinogenaemia, factor IX deficiency, haemophilia, Von Willebrand's disease, Disseminated Intravascular Coagulation [DIC], fibrinogen deficiency, or other clotting factor deficiency)
12. Evidence at the time of Screening of significant renal or hepatic insufficiency (unless due to haemolysis, or leukaemic infiltration) as defined by any of the following local lab parameters:
  - a. Calculated glomerular filtration rate (GFR; using the Cockcroft-Gault equation)  $< 40$  mL/min or serum creatinine  $> 1.5$  x the local upper limit of normal
  - b. Aspartate transaminase (AST) or alanine aminotransferase (ALT)  $\geq 2$  x the local upper limit of normal
13. Known human immunodeficiency virus (HIV) infection or known active Hepatitis B or Hepatitis C virus infection (testing will not be conducted as part of Screening procedures).

**For Italy ONLY**, Exclusion 13 reads: Active infection with hepatitis B virus (positive hepatitis B surface antigen; **note:** positive hepatitis B surface antibody and positive hepatitis B core antibody are not exclusionary provided disease is not active, which should be clearly documented in the patient's medical history) or C virus (patients with positive hepatitis C antibody result would require confirmation of active disease with a positive hepatitis C polymerase chain reaction (PCR) test), seropositivity for human immunodeficiency virus (HIV).

14. History of any illness/impairment of gastrointestinal (GI) function that might interfere with drug absorption (e.g., chronic diarrhea), confound the study results or pose an additional risk to the patient by participation in the study; patients with gastric bypass surgery.
15. Use of an investigational agent within less than 14 days, or the equivalent of at least 7 half-lives of that agent, whichever is the longer, prior to study Day 0.
16. Pregnant or lactating females; females intending to become pregnant at any time during the study.

**GUIDELINES:** These guidelines are for use by the Investigator, study staff and patient to safeguard patient safety while maintaining data integrity. Please contact the Medical Monitor with questions.

1. In general, supportive care (transfusions, administration of anti-fungals, etc.) should be maintained in accordance with institutional policy. Additionally:
  - a. It is advised that patients with a platelet count  $\leq 10 \times 10^9/L$  (10 k/ $\mu$ L) be transfused.
2. Hydroxyurea may be used during the study in case of proliferation as follows:
  - a. At the PIs discretion, initiate hydroxyurea treatment for white cell count  $\geq 30 \times 10^9/L$  (30,000/ $\mu$ L) and majority of cells appear to be immature cells (myelocytes/promyelocytes)
  - b. Discontinue hydroxyurea treatment when white cell count is  $< 10 \times 10^9/L$  (10,000/ $\mu$ L)
3. Patients taking medications that have the potential to induce or inhibit CYP3A4 or CYP2D6 should be monitored closely for potential effects of co-administration; particular attention should be given to anti-infectives in the azole class.
4. Cessation of IMG-7289 is invariably associated with a rebound in thrombopoiesis and platelet counts may easily exceed the baseline in any given patient. When IMG-7289 is discontinued, the platelet count should be monitored closely and the timing of the start of an alternative therapy should take this into account.

**PROHIBITED MEDICATIONS/TREATMENTS:** Please consult the Medical Monitor with any questions pertaining to prohibited medications.

1. All cytotoxic agents, with the exception of hydroxyurea
2. All haematopoietic growth factors: romiplostim, eltrombopag, granulocyte and granulocyte-macrophage colony stimulating factor (G-CSF and GM-CSF) and erythropoietin (EPO)
3. Prednisone or prednisolone  $> 10$  mg/day (noted exception: use of corticosteroids for management of gout is allowed) and dexamethasone  $> 4$  mg/day. Maintenance supplemental corticosteroid therapy such as prednisone  $\leq 10$  mg/day or corticosteroid equivalent is allowed.
4. Monoamine oxidase A and B inhibitors
5. Anticoagulant and nonsteroidal anti-inflammatory drug (NSAID; including aspirin) use are prohibited in patients when their platelet count is  $< 50 \times 10^9/L$  (50 k/ $\mu$ L)

**Management of Study Toxicities:** Adverse event intensity will be evaluated using the National Cancer Institute (NCI) Common Terminology Criteria for Adverse Events (CTCAE) version 4.03, published 14 June 2010. Please refer to Section 8.2 for additional detail on management of study toxicities, including reduction of the starting dose based on DLT.

**Definitions:**

*Haematologic Toxicity:* Haematologic values outside of the normal reference range are inherent features of MPNs, and are expected effects of many therapeutic attempts to manage these diseases. The effects of IMG-7289 on normal myeloid haematopoiesis observed in non-clinical and clinical studies are expected in humans; these are pharmacodynamic effects of LSD1 inhibition by IMG-7289, thus not regarded as adverse. These events, with the exceptions below, will not be considered DLTs.

*Dose limiting toxicity (DLT):* Any one of the following AEs that occurs through Day 7 of the Initial Treatment Period and is considered by the Investigator to be possibly, probably or definitely related to IMG-7289:

- Thrombocytopenia leading to clinically significant sequelae (i.e., a clinically significant bleeding event\* or the need for prophylactic transfusions);
- A clinically significant bleeding event\* in a patient with a platelet count  $> 50 \times 10^9/L$  (50 k/ $\mu$ L);
- Any Grade 4 or 5 non-haematologic adverse event;

- Any Grade 3 non-haematologic adverse event with failure to recover to Grade 2 within 7 days of drug cessation, with the following exceptions:
  - ≥ Grade 3 nausea, vomiting or diarrhea that responds to standard medical care
  - ≥ Grade 3 asthenia lasting less than 14 days
- Any Grade 3 electrolyte abnormality unrelated to the underlying malignancy and persisting greater than 24 hours.

\*A clinically significant bleeding event is defined as an event that is life-threatening, cannot be controlled and/or results in haemodynamic instability.

Patients who experience a DLT may have their dose adjusted downward if the Medical Monitor and Principal Investigator deem it safe for the patient to continue on IMG-7289.

Please consult the Medical Monitor for IMG-7289 dose modifications for the management of clinically significant changes in platelets, neutrophil counts, or other haematologic parameters.

Expected toxicities with IMG-7289 are reported in the latest edition of the Investigator's Brochure.

**Stopping Rules:** IMG-7289 will be discontinued in the event of the following:

- Post DLT, the Medical Monitor and Principal Investigator deem it unsafe for the patient to continue on IMG-7289.
- Post dose reduction due to DLT, the patient fails to demonstrate significant improvement within 21 days.

CCI

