**Note:** In Germany, use of computerised tomography (CT) is not permitted for patients unable to undergo magnetic resonance imaging (MRI). Only MRI is permitted for study purposes.

Clinical laboratory measures: The following laboratory measures will be performed at Screening, Baseline (if separate from Screening visit), pre-dose Day 0, upon suspicion of relapse, at the EoT, pre-EoS, and EoS/ET visits, and in accordance with the below:

- Biochemistry – monthly (i.e., Days 28, 56, 84, 112, 140 and 168) throughout the study
- Haematology – every clinic visit throughout the study
- Coagulation – monthly (i.e., Days 28, 56, 84, 112, 140 and 168) throughout the study
- Urinalysis – Day 84 and Day 168 throughout the study

CCI [REDACTED] Sample collection time-points are below.

- Pre-dose Day 0, Days 14, 28, 84 and 168, and each Day 168 visit of the ATP, for as long as the patient continues to qualify
- At EoT, and at ET (ET required only if the patient discontinues during the ITP)

Red Cell Haemoglobin F (HbF) and %F cells (Selected sites only/ITP only):

- Pre-dose Day 0, Day 84 and Day 168
- At EoT and ET (both required only if the patient discontinues during the ITP)

CCI [REDACTED]

\*Any bone marrow aspirate samples will undergo genomic analysis as per the bone marrow sampling schedule.

CCI [REDACTED]

Blood, bone marrow and/or their contents may be retained for future exploratory studies.

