#### **7.2.6 Interruption of Dosing**

Patients requiring a Dose Hold according to the Titration and Rechallenge Rules, or due to an (S)AE, should be monitored at least weekly for safety purposes and to enable re-challenge to commence as soon as counts return to the required level, if it safe to do so. During these visits, patients are required to undergo complete blood counts only.

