## 9 STUDY ASSESSMENTS

This section provides comprehensive detail on the visits and assessments required; this section should serve as the main guidance for use during study visits. The Schedule of Assessments (Section 16.1) contains these details in schematic form, and is provided for use in a supportive/reference capacity only. In an effort to maintain clarity while facilitating a modicum of brevity, the 'Terms' in **Table 4** below will be utilized in this section to encompass the broader 'Protocol Meaning' as stated.

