### 9.3.1 ITP Day 0 – Treatment Start

#### 9.3.1.1 ITP Pre-Dose Day 0

- Update medical/medication history with any changes since Screening
- Limited PE, including Vital Signs

- Collect the completed copies of the MPN-SAF TSS, and provide patient with the MPN-SAF TSS **7-DAY RECALL** tool for completion prior to arriving for, or at their Day 7 visit
- Full Local Laboratory Assessment
- Urinalysis

CCI

- Perform abdominal MRI (or CT if the patient is not a candidate for MRI) within a  $\pm 2$  day window
- Dispense doses sufficient until the next visit and provide Dosing Instructions
- Ensure patient continues to meet eligibility criteria prior to dosing

**Note:** In Germany, use of computerised tomography (CT) is not permitted for patients unable to undergo magnetic resonance imaging (MRI). Only MRI is permitted for study purposes.

#### 9.3.1.2 ITP Dosing Day 0

- Administer Study Drug

#### 9.3.1.3 ITP Post-Dose Day 0

- Patients should remain in clinic for at least 2 hours post first dose
- Query for Adverse Events, using non-directive questions (i.e., "How are you feeling")
- Schedule Day 7 clinic visit

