#### 9.3.2 ITP Weekly Visits - Days 7, 14, 21, 28, 35, 42, 49 and 56 ( $\pm 2$ days)

- Limited PE, including Vital Signs
- Adverse Events and Concomitant Medications
- Collect MPN-SAF TSS and provide the MPN-SAF TSS **7-DAY RECALL** tool to patient for completion prior to arriving for, or at the next visit
- Pre-dose: Perform haematology assessment and determine if dose titration is required in accordance with:
  - **Amendment 6 patients:** Refer to Section 7.2.3.2, and utilize:
    - **Table 2** for Days 7, 14 and 21
    - **Table 3** for Day 28 and onward
  - **Continuing Amendment 5\* patients:** Refer to Section 7.2.3.1, and utilize:
    - **Table 1**
- Pre-dose: Perform drug accountability and collect study medication
- Dispense doses sufficient until the next visit and provide Dosing Instructions
- Schedule next clinic visit

\*Amendment 5 patients must complete the Initial Treatment Period and transition to Amendment 6 titration and re-challenge rules upon commencing the Additional Treatment Period.

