### 9.3.2.1 ITP Days 7, 21, 35, 42 and 49 only

- Pre-dose: Blood sample for haematology

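### No biochemistry is scheduled after the first dose until Day 28, so a DLT that shows only in the chemistry cannot be first detected by a scheduled test in the Day 0-7 window

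*Protocol*

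**What the plan says.** The Synopsis (Definitions) sets the DLT window as "Any one of the following AEs that occurs through Day 7 of the Initial Treatment Period" and requires the Investigator to judge the event possibly, probably or definitely related. Five criteria follow. Two concern thrombocytopenia and bleeding. The other three are any Grade 4 or 5 non-haematologic event, a Grade 3 non-haematologic event that does not improve within a week of stopping drug, and "Any Grade 3 electrolyte abnormality unrelated to the underlying malignancy and persisting greater than 24 hours". Protocol Section 11.2 lists clinically significant laboratory abnormalities among adverse events, so a DLT need not produce symptoms.

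The Synopsis (clinical laboratory measures) gives the on-treatment schedule: "Biochemistry – monthly (i.e., Days 28, 56, 84, 112, 140 and 168) throughout the study". Section 9, which states that "this section should serve as the main guidance for use during study visits", agrees with it:

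- Section 9.3.1.1 places a "Full Local Laboratory Assessment" on Day 0, before the first dose.
- Section 9.3.2 sets the "ITP Weekly Visits - Days 7, 14, 21, 28, 35, 42, 49 and 56", each with a window of ±2 days.
- Section 9.3.2.1 gives the laboratory requirement for Days 7 and 21 as "Pre-dose: Blood sample for haematology".
- Section 9.3.2.2 adds only a cytokine sample on Day 14.
- Section 9.3.2.3 brings back the full local panel, which includes biochemistry, on Day 28.

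For visits during a dose hold, Section 7.2.6 says: "During these visits, patients are required to undergo complete blood counts only".

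**The concern.** The plan defines a toxicity event that may be visible only in a chemistry result, and closes the window for it on Day 7. It then schedules no chemistry between the first dose and the end of that window. The one visit scheduled in the window after Day 0 already includes a blood draw, but for haematology alone.

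A DLT can lead to dose reduction or discontinuation for that patient (Synopsis, Definitions; Section 8.2.3). If the event is not seen, that decision is not prompted and daily dosing continues. Safety and tolerability is also a primary objective, so the study report needs to be clear about which DLTs the schedule was able to find.

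**Working it through.** No sample-size or error-rate figure is involved. The check sets the laboratory schedule against the DLT window.

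**Required draws in the window.** Biochemistry in the ITP falls on Day 0 (pre-dose), then on Days 28, 56, 84, 112, 140 and 168. That is 6 post-dose draws, and 0 of the 6 fall on or before Day 7. The Day 0 sample precedes exposure and cannot show a drug effect.

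**Timing of the first post-dose draw.** The Day 28 visit may fall from 28 − 2 = Day 26 to 28 + 2 = Day 30. Relative to the end of the window, that is 26 − 7 = 19 to 30 − 7 = 23 days late.

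**Doses already taken.** The sample is pre-dose. On Day 26 the patient has taken the doses of Days 0-25, which is 26. On Day 30 the patient has taken those of Days 0-29, which is 30.

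**Visits that could have carried it.** Three weekly visits precede Day 28 (Days 7, 14 and 21). All three draw blood and none requires biochemistry. The Day 7 visit may fall from 7 − 2 = Day 5 to 7 + 2 = Day 9, so it can land after the window has closed.

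**Other routes to a required panel.**

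- End of Treatment and Early Termination (Sections 9.6.1 and 9.6.3) include the full local panel, but only for a patient who stops.
- The Suspected Relapse visit (Section 9.5) includes it too, but relapse must follow a remission, and Section 16.7 requires a response to last at least 12 weeks.
- A dose hold adds weekly blood counts and no chemistry, even when the hold is for an adverse event (Section 7.2.6).
- Unscheduled visits (note to Table 4) and local testing beyond the minimum panel (Section 10.1) are possible but not required.

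**Criteria touched with uninterrupted dosing.**

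- Grade 3 electrolyte abnormality: yes.
- Grade 4 non-haematologic laboratory event: yes. Grade 5 is death and cannot be silent.
- Grade 3 non-haematologic event without recovery: no, because it is judged after drug has been stopped. It comes into play only after a hold, where blood counts alone are required.
- Thrombocytopenia with sequelae, and bleeding: no. These rest on clinical events and on counts taken at each visit.

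The result is 2 of 5.

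**What the gap covers.** It concerns first detection. The persistence of more than 24 hours need not be shown by Day 7, and Section 11.2 already requires follow-up of a clinically significant abnormality once it is known.

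**The case against.** The strongest reply concerns weight. Sections 8.2.2 and 8.2.4 and the schedule in Section 16.1 are redacted, so a DLT work-up may exist that cannot be read here. The Day 7 visit includes a limited examination and an adverse-event query, and investigators may test at any time. An abnormality that persists would appear on the Day 28 panel. The drug is also not new to patients at this dose: the earlier AML/MDS study treated up to 6.0 mg/kg/d with no safety signal reported, ten times the 0.6 mg/kg/d start, and in this trial the mean maximum dose had already reached 0.86 mg/kg (Section 5.1). Titration runs on platelets, neutrophils and haemoglobin, and the safety committee reviews data at least quarterly.

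Most of this stands and limits the severity. The redaction of Section 16.1 matters least, since Section 9 takes precedence over it and is readable. The redaction of Sections 8.2.2 and 8.2.4 is a real limit on what can be said. None of the other arguments puts a scheduled chemistry test inside the window.

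A reader might infer several stronger things that the documents do not support:

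- *That electrolytes are never measured.* The readable biochemistry list in Section 10.1.1 names none, but a redaction follows it, and the chemistry list in SAP Section IX.C is not exhaustive.
- *That a report of no chemistry DLTs would carry no information.* The Day 7 query and the Day 28 panel would still reveal symptomatic or persisting events.
- *That three of the five criteria are affected.* The third depends on stopping drug.
- *That the committee's completed 7-day review of 0.5 mg/kg/d was unsound.* It took place under an earlier visit schedule, which is not shown.

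**Conclusion.** The point holds as a minor gap in safety monitoring. For a patient who stays on treatment, the readable protocol requires no biochemistry from the first dose until Day 26-30, which is 19-23 days after the DLT window closes and after 26-30 doses. Within the window, no scheduled test can first detect an asymptomatic Grade 3 electrolyte abnormality or an asymptomatic Grade 4 non-haematologic laboratory event. An abnormality that persists is found late, and one that resolves before Day 28 could be missed.

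This rests on the readable text of the Synopsis and Section 9, which agree with each other. Confidence is high for that schedule. It is lower for any wider claim that such events go unassessed, because of the redacted DLT sections and the scope for discretionary testing. Nothing readable points to a specific electrolyte risk with this drug, and no readable efficacy analysis or sample-size statement uses a DLT count. It would therefore be wrong to read this as a threat to the titration scheme or the spleen results.

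**What to change.** 1. Add biochemistry, including serum electrolytes, to the existing ITP Day 7 blood draw in Section 9.3.2.1 and in the Synopsis laboratory schedule.
2. Confirm that serum electrolytes are in the Section 10.1.1 panel, and add them if they are not.
3. Take the Day 7 chemistry sample on or before Day 7 where possible (Days 5-7 of the permitted Days 5-9). This keeps the DLT definition as it is and avoids stretching the window to fit a late visit.
4. Repeat any Grade 3 electrolyte value more than 24 hours later, including during dose holds, where Section 7.2.6 now asks for blood counts only. This makes the general follow-up duty in Section 11.2 specific to the criterion.

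A single draw will not find an abnormality that arose and resolved before it, but it puts one scheduled test inside the window.

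The cost is one extra tube at a venepuncture already planned, a few more local laboratory values per patient to enter and review, and an occasional unscheduled repeat. It also needs a protocol amendment with the usual ethics approvals across approximately 25 sites in five countries, so it is best combined with the next planned amendment. If the schedule stays as it is, the clinical study report should state that non-haematologic DLTs visible only in laboratory results were not systematically assessed in the window.
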